### Basic Demographics

Pre-operation baseline demographics will be collected for inter-patient comparisons:

1. Gender
2. Age
3. Height, Weight and Body Mass Index
4. Duration of Symptomatic Knee OA
5. Ethnicity

### Knee Function Assessment

#### 1. Speed of motion

The 10-meter timed walking test is a well-established and documented test for assessment for gait speed in patients. However, due to space limitations and the exhaustive nature of the test for patients with OA, the **6-meter test timed walking gait test** has been documented to be a valid and reliable substitute. Patients will be asked to walk a straight line of 6 meters where the time taken to complete the distance will be measured. (<7.5 seconds is normal).

The **Time up and go test (TUG)** is to determine fall risk and measure the progress of balance, sit to stand and walking. Patients will be asked to stand up from a chair, walk as quickly as possible in their a safe and most comfortable gait until they pass to 3 meters (10 feet) end of marked course with both feet. Turn around and walk back to the chair, time will be counted to the moment until the back of patients touches the back of the chair. ( $\leq 10$  seconds = normal;  $\leq 20$  seconds = good mobility, can go out alone, mobile without gait aid;  $\leq 30$  seconds = problems, cannot go outside alone, requires gait aid;  $\geq 14$  seconds indicates high risk of falls)

#### 2. Range of motion

The **active range of motion test** predicts the mobility of the joint by measuring the amount of active knee extension and flexion. "For measurement using the goniometer, 1 arm of the goniometer is placed parallel to the shaft of the femur lining up with the greater trochanter, and the other arm is placed parallel to the shaft of the lower leg lining up with the lateral malleolus of the fibula. The axis of the goniometer is placed over the lateral femoral epicondyle. Knee extension: The patient is supine. The heel of the limb of interest is propped on a bolster, assuring the back of the knee and calf are not touching the support surface. The patient is asked to actively contract the quadriceps. The amount of knee extension is recorded with the goniometer. Knee flexion: The patient is prone. The patient flexes the knee as far as possible. The amount of knee flexion is recorded with the goniometer."(15)

### 3. Knee Stability test

**KT-1000** will be used at the assessing of knee laxity as it provides an objective evaluation of knee stability resulting from the automated anterior drawer test it performs.

### 4. Knee extensor/flexor strength

Muscle strength on the quadriceps is measured by instructing the patient to perform an active knee extension movement in a sitting position with both feet free from ground, and the hip and knee joint flexed at 90%. The optimal isometric force of the knee extension/flexion movement is measured by the dynamometer attached at the malleoli level with a strap.

The measurements will be taken at maximum force for three times.

## Physical Activity Questionnaires

Patient's health related quality of life (HRQoL) will be assessed through three validated and reliable questionnaires (i.e. SF-12, WOMAC).

### 1. Short-Form 12 (SF-12)

The SF-12 health survey uses 12 questions to measure patient's functional health and well-being from a patient's point of view. It is reliable and validated measure that summarizes the patients' physical and mental health.

### 2. Western Ontario and McMaster Universities Osteoarthritis Index (WOMAC)

The WOMAC questionnaire is a questionnaire that measures patient's pain, stiffness and physical function and can be summed up into a score out of 96. A high score indicates a more disabled participant.

### 3. The Forgotten Joint Score-12

The FJS-12 comprise measures for the assessment of joint-specific patient-reported outcome in their ability to forget about a joint as a result of successful treatment. Joint awareness can be simply defined as any unintended perception of a joint. This may include strong sensation sensations like pain, but also includes more subtle feelings like mild stiffness, subjective dysfunction, or any discomfort.

### 4. Knee Society Score (KSS), Knee Society Function Score (KFS)

The KSS is an instrument assessing patient's pain and functionality based on a series of questions interviewed by a clinician. The validated questionnaire combines the objective physician derived component with a subjective patient derived component which evaluates pain, functionality, satisfaction and fulfillment of expectations. The results will be calculating the total score with 100 being the highest and 0 the lowest.

Physical Assessments	Prep-op	6 weeks	6 months	12 months
----------------------	---------	---------	----------	-----------

6m gait	✓	✓	✓	✓
TUG	✓	✓	✓	✓
Active ROM	✓	✓	✓	✓
KT-1000	✓	✓	✓	✓
Knee extensor/flexor	✓	✓	✓	✓
SF12	✓	✓	✓	✓
WOMAC	✓	✓	✓	✓
KSS & KFS	✓	✓	✓	✓
Compliance assessment	✓	✓	✓	✓
Satisfaction Survey	✓	✓	✓	✓

**Clinical Research Compliance assessment** will be conducted to measures the period and amount of time designated knee brace has been put on as interventional means. It is also recorded to the attendance of routine post-operative procedures of physiotherapy training one might receive.

**Patients satisfaction Survey** is to be recorded in terms not only how well to the quality of care patient was being treated, but to also the content a patient is with the care they received.

#### **Data Processing and Statistical Analysis:**

Demographic characteristics will be demonstrated using Student t-test or Chi-square test for continuous data and categorical data respectively where appropriate. The accuracy of primary measurements between the treatment (proprioceptive knee brace + routine post-operative procedures) and control (routine post-operative procedures) groups at the 4 time points (Pre-operative, 6 weeks, 6 months, 12 months) will be compared using ANOVA. Secondary outcomes and different types of patient-oriented quality of life questionnaires collected at the 4 time points will be compared using ANOVA likewise. All statistical analysis will be carried out using IBM SPSS version 25 (Armonk, NY:IBM Corp).

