**E. Plan of Investigation:**

30 patients with end stage knee OA who are schedule for TKA will be recruited via face to face promotion from the Li Ka Shing Orthopaedics Specialist clinic at the Department of Orthopaedics and Traumatology at Prince of Wales Hospital (PWH) Hong Kong. 15 patients will be randomly allocated to each of the treatment (proprioceptive knee brace + routine post-operative procedures) and control (routine post-operative procedures) groups.

Part 1a. Preliminary assessment on patients from Prince of Wales Hospital Orthopaedics specialist clinic based on inclusion and exclusion criteria

Part 1b. Preliminary assessment on patients [i.e. Basic demographics, Knee Function Assessment, Outcome Measurement Questionnaires]

Part 1c. Randomise allocation between treatment and control group

Part 2. Peri-operative assessment [i.e. Length of Hospital Stay]

Part 3. Distribution of knee brace (available to treatment arm) post-operative 2 to 4 week recovery

Part 4a. Post-operative 6 weeks Assessment

Part 4b. Post-operative 6 months Assessment

Part 4c. Post-operative 12 months Assessment

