**F. Methods:**

**(1) Post recruitment assessment**

After recruitment, oral and written consents will be obtained from individuals who agree to participate in the study. The recruitment period will last for 12 months and the whole project period is 2 years in total. Basic Demographics, Knee Function Assessment and Physical Activity Questionnaires will be carried out.

Inclusion criteria - Patients are included in the experiment if

- (1) Adult (age over 18 years old) underwent Total Knee Arthroplasty within 2 to 4 weeks;
- (2) Adult who is able to provide written consent and compliance with treatment and assessment regime

Exclusion criteria - Patients are excluded from the experiment if

- (3) Patients with disabilities, wheelchair dependence for mobility;
- (4) Underwent revision Total Knee Arthroplasty;
- (5) Found with complication wounds following surgery;
- (6) Diagnosed with comorbidities e.g. inflammatory arthritis, obesity, dermatological disorders that might affect their compliance to treatment;
- (7) Do not fit to the sizes of knee braces;
- (8) Not to give written consent and be non-compliance with the treatment and assessment regime

Sample Size Estimation

The sample size estimation was calculated using GPower 3.1 based on the yearly admission total knee replacement cases at Prince of Wales hospital. Effect size was calculated at 0.5. With 95% power and an alpha value of 0.05, 12 participants are required for each of the study control and intervention groups. An additional 25% will be added to account for possible attrition. Total 30 (15x2) subjects will be recruited for this study.

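### The pre-operative value is compared between arms as an outcome instead of being used as a covariate: a small, cheaply recovered loss of precision

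*Protocol*

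**What the plan says.** The Protocol's statistical section says of the primary measurements that the "groups at the 4 time points (Pre-operative, 6 weeks, 6 months, 12 months) will be compared using ANOVA". It extends this to the rest: "Secondary outcomes and different types of patient-oriented quality of life questionnaires collected at the 4 time points will be compared using ANOVA likewise". It does not say which ANOVA is meant or which term is tested, and it names no baseline covariate.

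Section E puts preliminary assessment and randomisation before surgery, and the brace after it: "Part 3. Distribution of knee brace (available to treatment arm) post-operative 2 to 4 week recovery". The schedule of assessments plans a pre-operative value for 6 m gait, TUG, active ROM, KT-1000, strength, SF-12, WOMAC and KSS/KFS.

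The point of entry is described in two ways. Section E says "30 patients with end stage knee OA who are schedule for TKA will be recruited". The first inclusion criterion in Section F reads "Adult (age over 18 years old) underwent Total Knee Arthroplasty within 2 to 4 weeks". Section F also places the assessments after recruitment: "Basic Demographics, Knee Function Assessment and Physical Activity Questionnaires will be carried out".

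**The concern.** A value measured before the brace is given cannot respond to the brace. Under randomisation, a test of the arms on that value tests a null hypothesis already known to be true. What the value can do is explain between-patient variation at the later visits, and the plan as written does not give it that role.

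The consequence depends on which ANOVA is meant:

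- **One test per visit.** The post-operative comparisons are valid but ignore the pre-operative value.
- **Group-by-time.** The pre-operative value is used, in effect as a change from baseline. This is valid, but inefficient when the pre-to-post correlation is low.
- **Group main effect over all four visits.** A sustained effect is averaged with a visit at which it must be zero.

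The sample size paragraph counts on 12 analysed patients per arm, so precision is scarce and information already collected should be used.

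**Working it through.** **Inputs from the Protocol.** 12 analysed per arm ("12 participants are required for each of the study control and intervention groups"); alpha 0.05; "Effect size was calculated at 0.5"; four visits, the first before the brace.

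**Assumptions.** Two-sided test; SD 1 at every visit; pre-to-post correlation a = 0.2, 0.3, 0.5 or 0.7; correlation between post-operative visits b = 0.5 or 0.7; the same effect d at all three post-operative visits. The Protocol does not say whether 0.5 is a standardised difference or Cohen's f. For two groups f = 0.5 means d = 1.0, so both d = 0.5 and d = 1.0 were tried.

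**The plan's own figure.** For two groups at d = 0.5 and 95% power, n per arm = 2(1.960 + 1.645)² / 0.5² = 104 (105 by the t distribution). At d = 1.0 it is 27. Neither is 12. That is a separate problem; 12 per arm is taken here as given.

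**Single visit, variance of one patient's analysed value**

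- Visit-by-visit ANOVA: 1
- Change from baseline: 2(1 − a)
- Pre-operative value as covariate: 1 − a², with one degree of freedom lost and a penalty for chance baseline imbalance

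The standard error of the group difference is √(variance × 2/12). For the unadjusted test at d = 1.0 this is 0.408. The noncentrality is 1.0/0.408 = 2.45 on 22 degrees of freedom, and power is 65%. For the covariate at a = 0.5 the variance is 0.75. Power is 77% if chance imbalance is ignored and 75% once it is averaged in.

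| | a = 0.2 | 0.3 | 0.5 | 0.7 |
|---|---|---|---|---|
| d = 1.0, visit-by-visit | 65% | 65% | 65% | 65% |
| d = 1.0, change from baseline | 46% | 51% | 65% | 86% |
| d = 1.0, covariate | 64% | 67% | 75% | 89% |
| d = 0.5, visit-by-visit | 22% | 22% | 22% | 22% |
| d = 0.5, change from baseline | 15% | 17% | 22% | 33% |
| d = 0.5, covariate | 22% | 22% | 26% | 36% |
| 95% CI half-width (SD), visit-by-visit | 0.84 | 0.84 | 0.84 | 0.84 |
| 95% CI half-width (SD), change | 1.06 | 0.99 | 0.84 | 0.65 |
| 95% CI half-width (SD), covariate | 0.84 | 0.82 | 0.74 | 0.61 |

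Simulation (40,000 trials per setting) and the noncentral distributions agree to within about one percentage point. Type I error was 4.9 to 5.2% for all three analyses. Covariate and visit-by-visit power are equal at a = 0.222 (d = 1.0) and a = 0.218 (d = 0.5).

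**Main effect over four visits.** The expected estimate is (0 + d + d + d)/4 = 0.75d, whatever the correlation. With a common correlation r between all visits the variance is (1 + 3r)/4. Power at d = 1.0 is then 72, 60 and 51% at r = 0.3, 0.5 and 0.7.

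**Post-operative average (not planned, but one possible main estimate).** The variance is (1 + 2b)/3 unadjusted, and adjustment removes a². The share removed, a²/((1 + 2b)/3), and power at d = 1.0 are:

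- a = 0.2, b = 0.5: 0.04/0.667 = 6%; power 82% to 82%
- a = 0.3, b = 0.7: 0.09/0.80 = 11%; power 74.6% to 77.5%
- a = 0.5, b = 0.5: 0.25/0.667 = 38%; power 82% to 94%

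If a 1.0 SD effect is present at 6 weeks only, the adjusted average has 15 to 28% power, against 64 to 89% for the adjusted 6-week comparison.

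**The case against.** Only the Protocol was available. Covariates, the type of ANOVA and the tested term often belong in an SAP, so their absence is not in itself an error. The two natural readings are valid, and group-by-time already uses the pre-operative value. The pooled main effect, the only reading that biases the estimate, is nowhere stated. The benefit rests on an assumed correlation, which surgery may weaken. At d = 0.5 there is essentially no gain at correlations of 0.2 or 0.3. The entry conflict is an eligibility matter in its own right. Finally, the power figures are for single visits and an average, not for a three-visit mixed model with one shared baseline slope.

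Most of this stands, and it is why the point is minor. Two parts do not remove it. The Protocol is not silent: it fixes the pre-operative visit as one of four compared time points, and an SAP that used it as a covariate would depart from that sentence. And with complete data, an unstructured covariance and a baseline-by-visit term, the mixed model gives the single-visit covariate-adjusted differences, so the tabulated comparison is relevant to it.

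**Conclusion.** The concern holds as a minor efficiency point. The pre-operative value is given the role of an outcome when its useful role is that of a covariate. At a single visit, for a sustained effect and correlations of 0.2 to 0.7, covariate adjustment is about equal to or better than both valid readings. At 1.0 SD its difference from visit-by-visit ANOVA runs from −1 to +24 percentage points of power (64 − 65 to 89 − 65). Against change from baseline the gain runs from 18 points at a correlation of 0.2 (64 − 46) down to 3 points at 0.7 (89 − 86). The gain is likely but not certain, because the Protocol gives no correlation. If a four-visit main effect were meant, the estimate of a sustained effect would also shrink by a quarter.

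Adjustment does not rescue the sample size: at 0.5 SD, single-visit power is 36% or less under every analysis considered. The figures assume normal data, equal SDs, 12 complete patients per arm and a pre-operative value for each of them. The entry wording does not guarantee that last condition.

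**What to change.** For each continuous outcome with a scheduled pre-operative value, analyse the 6-week, 6-month and 12-month values in a linear mixed model. Include group, visit, group-by-visit and the pre-operative value of the same outcome; a baseline-by-visit term lets its slope differ between visits. Report the adjusted group difference with a 95% CI at each visit, and name one main estimate in advance. A post-operative average is a poor choice if the effect is expected only at 6 weeks. Do not test the arms on the pre-operative value as an outcome.

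Reconcile Section E with the inclusion criterion in Section F on whether patients enter before or after surgery. The covariate exists for everyone only if all patients are assessed before surgery.

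The FJS-12 (no row in the schedule), satisfaction with care and complications are outside this change, and the stated sample size is a separate matter. The cost is a few lines of analysis wording plus the reconciled entry text; visits and software stay the same.

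### The Protocol expects attrition but fixes an unspecified ANOVA over four visits; either form of it uses partly observed patients less well than a mixed model in the same software

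*Protocol*

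**What the plan says.** Under Data Processing and Statistical Analysis, the Protocol states for the primary outcome that the treatment and control "groups at the 4 time points (Pre-operative, 6 weeks, 6 months, 12 months) will be compared using ANOVA". Secondary outcomes and questionnaires "collected at the 4 time points will be compared using ANOVA likewise". On software it says: "All statistical analysis will be carried out using IBM SPSS version 25".

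Section F (Sample Size Estimation) expects losses. It says "With 95% power and an alpha value of 0.05, 12 participants are required for each of the study control and intervention groups", then "An additional 25% will be added to account for possible attrition", and concludes "Total 30 (15x2) subjects will be recruited for this study".

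The assessment table after the Knee Society Score text schedules every listed measure at all four visits, so each patient supplies up to four values per outcome. In Section E the pre-operative assessment comes before allocation, and the brace is handed out only after surgery.

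The Protocol does not say whether the ANOVA is repeated-measures or run visit by visit. It names no method that would keep a partly observed patient in a joint analysis of the visits.

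**The concern.** The method named fits poorly with the attrition that the same document foresees. With four measurements per patient, repeated-measures ANOVA is one obvious reading. SPSS's GLM version of it takes one row per patient and deletes listwise. A patient measured before surgery, at 6 weeks and at 6 months who then withdraws would contribute nothing, even at the visits attended. The other reading, a separate ANOVA at each visit, keeps everyone seen at that visit but makes no use of what a withdrawn patient showed earlier.

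In a trial of 30 patients, outcome data already collected should not be discarded. Both forms also need missingness to be unrelated to the outcomes, including those already observed. Only one arm has a device that a patient may give up, so this assumption should not be made more demanding than necessary.

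**Working it through.** **The plan's own figure.** Attrition step: 12 × 1.25 = 15 per arm, 30 in total, which reproduces. Fifteen per arm leaves the planned 12 if up to 3/15 = 20% are incomplete. Whether 12 follows from the stated effect size and power is a separate question; nothing below depends on it.

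**Inputs.** From the Protocol: 15 per arm, 12 required, three post-operative visits (6 weeks, 6 months, 12 months). Assumed, because the documents give no figure: the pattern and rate of missed visits. All pre-operative values are taken as present. The standard error of the difference between arms at a visit is taken as proportional to 1/√n per arm, with equal arms and a common standard deviation.

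**Branch A: repeated-measures ANOVA with listwise deletion.**

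*Case A1, dropout.* Three of 15 per arm attend at 6 weeks and withdraw before month 12.
- At 6 weeks, 15 are observed and 12 analysed: √(15/12) = 1.118, so the standard error is about 12% higher than the data allow.
- At month 12, 12 are observed and 12 analysed: no observed patient is lost.

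*Case A2, scattered misses.* Each post-operative visit is missed independently with probability p.
- Complete cases per arm = 15(1−p)³.
- Seen at any one visit = 15(1−p).
- Share of those seen who are discarded = 1 − (1−p)².
- Standard error ratio = √[15(1−p) / 15(1−p)³] = 1/(1−p).

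| p (assumed) | complete per arm | seen per visit, per arm | seen but discarded | standard error ratio |
|---|---|---|---|---|
| 5% | 12.86 | 14.25 | 9.8% | 1.05 |
| 10% | 10.94 | 13.50 | 19.0% | 1.11 |
| 15% | 9.21 | 12.75 | 27.8% | 1.18 |

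For both arms together, complete cases are 25.7, 21.9 and 18.4 of 30. At p = 10%, about 8 of 30 patients are dropped (30 − 21.9 = 8.1), although only about 3 are missing at any one visit.

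*When the allowance runs out.* Twelve complete patients per arm require (1−p)³ ≥ 12/15 = 0.8, so p ≤ 1 − 0.8^(1/3) = 0.072, or about 7% per visit.

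**Branch B: separate ANOVA at each visit.** Patients analysed equal patients seen, so none of the losses in Branch A arise. What is given up is the information that a withdrawn patient's earlier values carry about later visits. Its size depends on the correlation between visits, which the documents do not give, so I put no figure on it.

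**Assumption on missing data.** Both branches compare arms without bias if, within arm, missingness is unrelated to the outcomes. A likelihood-based mixed model also allows missingness to depend on values already observed, such as a poor 6-week result. It is therefore less demanding under either reading.

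**The case against.** The strongest reply is that the Protocol never names repeated-measures ANOVA. Its sentence can equally be read as a between-arm test at each time point, and then no attender is dropped. That stands: the listwise deletion and every figure under Branch A are conditional. A reader might infer that the plan certainly discards incomplete patients; the text does not support that.

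Second, the 25% allowance already budgets for 12 completers per arm. This also stands. A reader might infer that the trial loses its planned numbers, but that happens only if more than 20% of patients miss at least one visit. The 10% and 15% rates and the independence of misses are illustrations. Dropout, where the same patients miss successive visits, costs less at the later visits.

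Third, it is tempting to say that patients who stop the brace will leave and so bias the comparison. The documents do not show this. They schedule a compliance assessment at every visit, so low brace use may be recorded in patients who still attend, and nothing says that patients who stop wearing the brace are no longer assessed. One-sided dropout remains a plausible risk of unknown direction and size.

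Fourth, missing-data handling may sit in a statistical analysis plan that is not shown. That would answer a complaint about a missing section. The point here concerns the method that the Protocol does name, which a mixed model improves on under either reading.

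Finally, a mixed model is not a cure: if patients leave for reasons not reflected in recorded values, it too is biased.

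**Conclusion.** The point holds in a limited form. The Protocol foresees attrition and fixes an ANOVA whose form is left open.

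- As repeated-measures ANOVA, it drops a patient with one missed visit from all visits of that outcome. The cost is about 12% on the 6-week standard error if 3 of 15 per arm withdraw after that visit and before month 12. At an assumed 10% independent missingness per visit, it is about 19% of attenders and 11% on the standard error.
- As a separate ANOVA per visit, it drops no attender but ignores earlier values of those who have left.

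Both forms rest on a stronger missing-data assumption than necessary. The loss of precision is modest and conditional, and bias is a possibility rather than a finding. The change is worth making because it improves on either reading at little cost.

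**What to change.** In Data Processing and Statistical Analysis, replace ANOVA for the repeated primary and secondary outcomes with a linear mixed model fitted in the SPSS MIXED procedure:

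- Outcomes: the 6-week, 6-month and 12-month values.
- Terms: arm, visit, arm-by-visit, and the pre-operative value as covariate. Section E places that value before allocation, so the brace cannot affect it.
- Data: all available visits of each randomised patient, analysed in the allocated arm.

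Say at what point a patient counts as randomised. Section E lists allocation before surgery, while some eligibility criteria in Section F can be judged only afterwards.

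The cost is a change of wording and of procedure within the software already named, with no extra patients or visits. There are three downsides. A covariance structure and a small-sample degrees-of-freedom method must be chosen in advance for 30 patients. A patient without a pre-operative value, or with no post-operative visit, still contributes nothing unless a rule is added. The model also still assumes that missingness is explained by the observed data.
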